6.3 Exclusion Criteria

1. Pre-ART viral load <2000 copies/ml (HIV controllers).
2. Based on prior history and/or virologic testing, no alternative ART regimens are available in the event that the current ART regimen is compromised as a result of this study.
3. Recent hospitalization in the last 90 days.
4. Recent infection in the last 90 days requiring systemic antibiotics.
5. Recent vaccination within the last 8 weeks prior to study screen or any study blood draw.
6. Any known prior (lasting >6 months) or current history of liver-related diseases including but not limited to:
 - a. Hepatic cirrhosis of decompensated chronic liver diseases
 - b. Clinically active hepatitis B or C infection as evidenced by clinical jaundice or Grade 2 or higher liver function test abnormalities
 - c. Any hepatic impairment, regardless of the graded liver function test abnormalities.
7. Any known prior (lasting >6 months) or current history of gastrointestinal diseases including but not limited to:
 - a. History of diarrheal illness requiring the use of anti-motility agents including inflammatory bowel disease, chronic diarrhea not otherwise specified.
 - b. History of gastrointestinal bleeding with hemoglobin below 12.5 g/dL.
 - c. History of gastric or duodenal ulcers
 - d. Inflammatory gastrointestinal disease such as Crohn's disease or ulcerative colitis
8. Any significant renal disease (eGFR < 90 ml/min) or acute nephritis.
9. Screening hemoglobin below 12.5 g/dL.

10. Screening TSH consistent with hypothyroidism.
11. Significant myocardial disease (current myocarditis or reduced left ventricular ejection fraction below the lower limit of normal) or diagnosed coronary artery disease.
12. Significant respiratory disease requiring oxygen.
13. Diabetes or current hypothyroidism.
14. Participants of reproductive potential or breastfeeding. Women of childbearing potential must have a negative serum pregnancy test at screening. All participants of childbearing potential must agree to use a double-barrier method of contraception throughout the study period and up to 90 days after the last dose of kansui.
15. Exposure to any immunomodulatory drug (including maraviroc) in the 16 weeks prior to study.
16. Prior or current use of experiment agents used with the intent to perturb the HIV-1 viral reservoir.
17. History of seizures, psychosis, abnormal electroencephalogram or brain damage with significant persisting neurological deficit
18. Positive test for tuberculosis by either skin test (PPD) or blood interferon-gamma release assay (QuantiFERON).
19. Significant substance use, which in the opinion of the investigator(s), is likely to interfere with the conduct of the study
20. Anticipated conflict or inability to attend and complete all protocol-scheduled study visits and assessments, especially for participants in Cohort 2 where treatment phases are separated by a 56-day washout

7 CONCURRENT MEDICATIONS

Participants may continue to take their usual medications, as long as they are medically necessary and can be monitored during the study period.

7.1 Allowed Medications and Treatments

Participants may not have exposure to any immunomodulatory drug (including maraviroc) in the 16 weeks prior to study or during study period and may not currently be taking experimental latent HIV reversing agents.

In the absence of drug-drug interaction information with kansui, only concomitant medications that are medically necessary will be continued with appropriate monitoring. In addition, the following medications are prohibited during the study and administration will be considered a protocol violation.

- Participants may not be take anti-motility agents during the study period. This is to allow accurate assessment of diarrhea-related adverse events.

- Participants may not initiate new medications that may cause diarrhea during the 31-day study period. These may include but are not limited to:
 - Proton pump inhibitors
 - Antibiotics
 - Antidepressants
 - Colchicine
 - Digitalis

In addition to the above medications, per traditional Chinese medicine practices, participants should also not ingest ice-cold food or beverages, spicy foods, or seafood in the two days prior to, during, and up to two days after kansui treatment.

8 STUDY TREATMENTS

8.1 Method of Assigning Participants to Treatment Groups

Cohort 1: NA

Cohort 2: Participants will be randomized to either kansui versus placebo treatment first using a random number generator. Whichever treatment the participant receives first, they will receive the other treatment (placebo or kansui) for their second treatment starting at Day 102 (See Study Events Table in Section 9 below).

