4 STUDY DESIGN

4.1 Study Overview

Prior trials evaluating latent reactivating agents have demonstrated that a “priming” period appears to yield greater latency reversal.^{5,7} Therefore, we will perform this multi-center, phase I clinical study of kansui in eight HIV-infected ART-suppressed participants as a dose escalation trial with a double-blinded, randomized, placebo-controlled crossover cohort. The first two participants will complete a kansui-only treatment phase in which they will be given a single, open label 1g dose of *Euphorbia kansui* extract powder prepared as tea. The second group of six participants will complete the study twice (once on a decaffeinated black tea placebo treatment arm and once with the kansui treatment arm) in a randomized, double-blinded, placebo-controlled crossover design. Which treatment arm occurs first will be randomly assigned and will include a 56-day washout period between the two phases. A second screening visit will occur immediately following the washout period on Day 88. The second screening visit will occur 14-days prior to starting the second treatment assignment on Day 102; the second treatment phase will therefore begin on Day 88 and end on Day 101 (See Study Events Table). As indicated by the dose-escalation design of the study, participants in the kansui treatment phase for group 2 will receive 3 consecutive daily 1g doses of *Euphorbia kansui* extract powder served as tea.

We propose using a crossover double-blinded design due to our experience in performing *in vivo* studies of latent HIV reactivation. We have previously demonstrated statistically significant inter-individual differences in baseline values of the virologic and immunologic outcomes proposed in our study.² For these reasons, we have applied a similar crossover study design in another recent study which allowed the ability to detect even small differences in HIV RNA levels after intervention.³⁵ Therefore, due to the small detectable changes that most HIV latent reactivating agents (LRAs) produce at the doses tested in these trials^{2,5,36,37} and the possibility of small detected changes from our trial of *kansui*, a within-subject control component to the study will allow us the greatest ability to accurately detect treatment-related differences in our study outcome measures.³⁸

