8.2 Blinding

Cohort 1: NA

Cohort 2: The order in which participants in Cohort 2 complete the two treatment phases (i.e., kansui and placebo) will be unknown to both the participants and the PI/study team. Both the kansui and placebo will be prepared and delivered to the Center for Clinical & Translational Science (CCTS) in identical, HDPE vials (described later in section 8.3.3). Upon arrival at the CCTS, the HDPE vial will be received by a CCTS study nurse. At the appropriate time, the CCTS study nurse will prepare the tea (either kansui or placebo) in the med room of the CCTS, out of sight of the study participant, study coordinator, and study site PI to maintain double blinding. Following preparation the study nurse will administer the tea (kansui/placebo) to the participant following protocol section 8.4.3. The University of Utah Investigational Drug Services (“UU IDS”) will randomize each participant in Cohort 2 according to the methods described in Protocol section 8.1. In the event that participant experiences an adverse event that requires the identity of the study drug be revealed, the PI will be able to contact UU IDS to break the blind. In the event that a participant blind is broken, the study PIs will determine the impact upon the unblinded subject’s continued participation in the study and if a replacement subject is needed on a case-by-case basis.

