14 STATISTICAL METHODS AND CONSIDERATIONS

14.1 Data Sets Analyzed

[name] will be performing the data analysis for the study. Paired analyses using Wilcoxon signed rank tests will be performed to evaluate whether there is a statistically significant change in markers of immune activation (CD69, CD38, and/or HLA-DR) on CD4+ and CD8+ T cells after a 1, 2, or 3 doses of *Euphorbia kansui* extract powder prepared as tea compared to baseline (reference will be the average of the three baseline measures). Multivariate analyses will then be performed to evaluate the association between kansui and measures of immune activation at post-dosing, using linear mixed effects models, which account for within-participant correlation of observations and allows for greater stability in the estimate of the outcome measures within individuals. Similarly, for measures of the HIV reservoir, we will perform linear mixed effects regression to compare CA-US RNA levels before and after kansui and use negative binomial mixed effects regression (a method to analyze over-dispersed count data) to compare plasma HIV RNA levels before and after kansui administration (reference will be the average of three baseline measures).

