14.4 Analysis of Secondary Endpoints

We will perform Wilcoxon rank sum tests to compare levels of immune activation (CD69, CD38, and/or HLA-DR expression on CD4+ and CD8+ T cells) between dosing cohorts and Wilcoxon signed rank tests to compare measures within individuals. We will perform linear mixed effects modeling to compare the effect of *Euphorbia kansui* extract powder prepared as tea on immune activation over time and account for repeated measures within individuals, compared to pre-treatment (using the average of three baseline measures). Similarly, we will perform linear mixed effects regression modeling to assess changes in CA-US RNA levels and use negative binomial mixed effects

modeling to changes in plasma HIV RNA levels, before and after kansui administration (the reference will be the average of three baseline measures).

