14.5 Sample Size

A total of 8 participants (2 in dosing cohort 1 and 6 in dosing cohort 2) will contribute to the analysis, with 8 or 25 timepoint measures, respectively. The within-individual variability will be reduced by repeated measurements post-dose. Based on existing data from our study population regarding the percent CD38+HLA-DR+ CD4+ T cells (standard deviation of 4.9%) in our study population and a paired, one sample, repeated measures analysis, we will have greater than 80% power to detect a 2.7% change in CD4+ T cell activation levels post-dose. Similarly, we will have greater than 80% power to detect a 17% change in cell-associated HIV-1 RNA and a 0.37% change in plasma HIV-1 RNA.

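### Section 8.1 specifies no sequence balance for the six Cohort 2 crossover participants; with independent 50:50 draws a 3:3 split would occur only 31% of the time

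*Combined protocol and SAP*

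**What the plan says.** Allocation is described in three places in the combined protocol and SAP.

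- Section 8.1: "Participants will be randomized to either kansui versus placebo treatment first using a random number generator". Each person then receives the other treatment from Day 102.
- Section 8.2: the investigational pharmacy "will randomize each participant in Cohort 2 according to the methods described in Protocol section 8.1", which points back to 8.1 and adds no scheme.
- Section 4.1: "Which treatment arm occurs first will be randomly assigned and will include a 56-day washout period between the two phases".

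None of these states an allocation ratio, a block size or a number per order. Section 14.5 gives the size: "A total of 8 participants (2 in dosing cohort 1 and 6 in dosing cohort 2) will contribute to the analysis". Section 11.3 replaces Cohort 2 participants who stop before Day 104, and 8.2 allows replacement after a broken blind. Neither says which order a replacement receives.

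Section 4.1 justifies the crossover on the ground that "a within-subject control component to the study will allow us the greatest ability to accurately detect treatment-related differences in our study outcome measures". The analysis sections do not name that contrast. Section 14.1 uses models "to compare plasma HIV RNA levels before and after kansui administration (reference will be the average of three baseline measures", and 14.4 models immune activation "compared to pre-treatment (using the average of three baseline measures". Neither names a period term, a sequence term or a kansui-versus-placebo comparison.

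**The concern.** A two-period crossover separates treatment from period only if both orders are populated, and it does so most efficiently when they are equal. With six people and no balancing rule, chance can leave one order nearly or wholly empty.

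A period shift is plausible here. The two dosing phases start 101 days apart (Day 1 and Day 102). The Study Events Tables give three pre-dose draws in Phase 1 (Day -14, Day -7, Day 1 hour 0) and two in Phase 2 (Day 88, Day 102 hour 0). Section 4.1 itself expects small effects, so a modest shift could matter against them.

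Timing matters too. An analysis model can still be amended before unblinding. A 6:0 allocation cannot be repaired once dosing has started, and the precision lost at 5:1 cannot be recovered.

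**Working it through.** The plan states no figure on sequence balance, so there is none to reproduce.

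**Inputs.** Six participants in the crossover (14.5). The probability of kansui first is taken as 0.5 with independent draws. This is an assumption: 8.1 says only that people are "randomized to either kansui versus placebo treatment first" by a generator. Carryover is taken as absent.

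**Step 1: probability of each split.** With k people in one order, P = C(6,k)/2^6, adding both directions.

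- 3:3: 20/64 = 31.25%
- 4:2: 30/64 = 46.9%
- 5:1: 12/64 = 18.75%
- 6:0: 2/64 = 3.1%

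So 5:1 or worse has probability 14/64 = 21.9%, and any imbalance 44/64 = 68.75%.

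**Step 2: unadjusted kansui-minus-placebo mean.** Let n1 be the number kansui-first, n2 the number placebo-first, T the treatment effect, and S the shift from Phase 1 to Phase 2. A kansui-first person's difference has expectation T − S; a placebo-first person's has T + S. The mean over six is T + S(n2 − n1)/6.

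**Step 3: period-adjusted estimate.** Average the two order-specific mean differences. S cancels whenever both orders are populated. The variance is proportional to (1/n1 + 1/n2)/4.

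| Split | Share of S left, unadjusted | (1/n1 + 1/n2)/4 | Variance relative to 3:3 |
|---|---|---|---|
| 3:3 | 0 | 0.1667 | 1.00 |
| 4:2 | 2/6 = 1/3 | 0.1875 | 1.125 |
| 5:1 | 4/6 = 2/3 | 0.300 | 1.80 |
| 6:0 | 6/6 = all | not defined | not estimable |

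In standard errors, √1.125 = 1.06 and √1.80 = 1.34, so increases of about 6% and 34%.

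**Step 4: the analysis as written.** Suppose the three-value reference is the set of Phase 1 draws, the only phase with three. A kansui-first change then carries no shift between phases, and a kansui-second change carries all of S. The mean change carries S × n2/6, which is 3/6 = one half even at 3:3. Balance alone therefore does not protect this analysis.

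**Step 5: what a restricted list achieves.** One permuted block of six, or three blocks of two, gives 3:3 with certainty. Blocks of four do so with probability only 4/6 = 66.7%, because the fifth and sixth people come from a new block and must differ.

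**The case against.** **The scheme is not stated.** A reader might infer that 8.1 prescribes simple randomisation. It does not. A random number generator is also how a blocked list is made, and drawing for each participant is compatible with working down such a list. What stands is that no balancing is specified, so independent draws would comply with the text.

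**The harm is usually modest.** A reader might also infer that period effects will be confounded with kansui. Under the stated assumption, 31.25% + 46.9% = 78% of allocations are 3:3 or 4:2, and 4:2 costs about 6% in standard error once period is modelled. Complete confounding needs 6:0. The documents give no size for a period shift, and 6.2 requires 36 months of suppression and 24 weeks without a regimen change, which plausibly limits drift without excluding it. All this stands as a limit on severity. It does not remove the 22% chance of 5:1 or worse, and no period term is planned.

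**The figures belong to an estimator that the plan does not name.** Correct. The 12.5% and 80% apply to a period-adjusted kansui-versus-placebo contrast. The within-person signed rank test in 14.4 could be applied to a kansui-minus-placebo difference, but the section does not say so. The point must therefore be joined to a change in section 14.

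**The outcomes are secondary.** Sections 3.1 and 5.1 make safety primary, and 14.3 summarises it by dosing cohort. However, the Synopsis lists the immunologic effect among the primary objectives and calls T cell activation the primary outcome in its sample size rationale, so the comparison is not incidental.

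**A balanced list can weaken the blind.** Participants start on separate days (4.1) and kansui is expected to cause diarrhoea (2.1), so staff may guess earlier orders and deduce later ones. A published rule giving each replacement the order of the person replaced would also reveal that order after the unblinding that 8.2 permits. Both points stand and shape the fix.

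**Conclusion.** The concern holds as a gap in specification. Section 8.1 leaves balance to chance, and if the draws are independent and 50:50, 3:3 occurs 31% of the time, 5:1 or worse 22%, and 6:0 3%. The consequence depends on the analysis. Without a period term, 1/3, 2/3 or all of any period shift enters a kansui-minus-placebo mean at 4:2, 5:1 and 6:0. With one, there is no bias at 4:2 or 5:1 but 12.5% and 80% more variance, and 6:0 cannot be resolved.

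These figures rest on independent equal-probability draws, no carryover, six completers, and a kansui-versus-placebo contrast that section 14 has yet to name. The size of the period shift is unknown, so the bias can be stated only as a fraction of it. The immunologic and virologic comparisons are affected; the safety summary is not. The change is worth making before the first Cohort 2 allocation.

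**What to change.** 1. **Section 8.1.** State that the investigational pharmacy generates and holds a concealed balanced list, three kansui-first and three placebo-first. Do not disclose the block structure to the study team; keep it in a document that only the pharmacy can see. Avoid blocks of four.
2. **Sections 8.2 and 11.3.** State that the pharmacy assigns replacements so as to keep the balance. Do not publish a same-order rule for cases where the replaced participant was unblinded.
3. **Sections 14.1 and 14.4.** Name a mixed model comparing kansui with placebo, with a period term, and say which pre-dose draws form the reference in each phase. Without this step the balanced list does not pay off.

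The cost is a few sentences, and 8.2 already gives the randomisation to the pharmacy. The downside is slight predictability of late allocations if earlier orders are guessed. With six people this cannot be removed entirely, but it is a smaller risk than an unrecoverable split.

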8.2 Blinding

Cohort 1: NA

Cohort 2: The order in which participants in Cohort 2 complete the two treatment phases (i.e., kansui and placebo) will be unknown to both the participants and the PI/study team. Both the kansui and placebo will be prepared and delivered to the Center for Clinical & Translational Science (CCTS) in identical, HDPE vials (described later in section 8.3.3). Upon arrival at the CCTS, the HDPE vial will be received by a CCTS study nurse. At the appropriate time, the CCTS study nurse will prepare the tea (either kansui or placebo) in the med room of the CCTS, out of sight of the study participant, study coordinator, and study site PI to maintain double blinding. Following preparation the study nurse will administer the tea (kansui/placebo) to the participant following protocol section 8.4.3. The University of Utah Investigational Drug Services (“UU IDS”) will randomize each participant in Cohort 2 according to the methods described in Protocol section 8.1. In the event that participant experiences an adverse event that requires the identity of the study drug be revealed, the PI will be able to contact UU IDS to break the blind. In the event that a participant blind is broken, the study PIs will determine the impact upon the unblinded subject’s continued participation in the study and if a replacement subject is needed on a case-by-case basis.

8.3 Formulation of Test and Control Products

8.3.1 Formulation of Test Product

For the current pilot study, we will use the same standardized batch of *Euphorbia kansui* extract powder studied in [name] laboratory at UCSF to perform the preliminary experiments described above. The *Euphorbia kansui* extract powder was purchased from Baoji F.S. Biological Development Company, and is Good Manufacturing Practice (GMP)-certified. The *Euphorbia kansui* root powder will be provided by the study investigator at UCSF and shipped in bulk to the University of Utah Health Investigational Drug Service (UUH IDS) Pharmacy. The *Euphorbia kansui* root extract powder is stored at the UUH IDS Pharmacy in a re-sealable plastic bag at room temperature, away from moisture and light exposure. Since the test product is in powder form, UUH IDS will prepare individual 1 g doses of *Euphorbia kansui* extract powder provided by the Department of Herbal Medicine at the American College of Traditional Chinese Medicine at UCSF. The details regarding these procedures can be found in the Standard Operating Protocol (SOP), *Euphorbia kansui* Extract Tea Preparation Guidance, for kansui preparation and administration. The University of Utah Health Investigational Drug Service Pharmacy is located at the Huntsman Cancer Hospital, [name].

8.3.2 Formulation of Control Product

Placebo tea will be prepared using Twinings English Breakfast 100% pure black decaffeinated tea. One packet of tea will be prepared and administered as for kansui tea (see section 8.4.3). Briefly, four ounces of boiled water will be cooled to 170-185° F and added to the tea bag in a cup. The tea will be stirred for approximately 30 seconds using a wooden stirring stick and allowed to cool for at least 5 minutes, reaching a temperature of less than or equal to 100° F, before administration. The placebo will be prepared in a separate room such that study participants will not observe differences in tea preparation and packaging.

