	
disease or ulcerative colitis
 
8. Any significant renal disease (eGFR < 90 ml/min) or acute nephritis.9. Screening hemoglobin below 12.5 g/dL.10. Screening TSH consistent with hypothyroidism.11. Significant myocardial disease (current myocarditis or reduced left ventricular ejection fraction below the lower limit of normal) or diagnosed coronary artery disease.12. Significant respiratory disease requiring oxygen.13. Diabetes or current hypothyroidism.14. Participants of reproductive potential or breastfeeding. Women of childbearing potential must have a negative serum pregnancy test at screening. All participants of childbearing potential must agree to use a double-barrier method of contraception throughout the study period and up to 90 days after the last dose of kansui.15. Exposure to any immunomodulatory drug (including maraviroc) in the 16 weeks prior to study.16. Prior or current use of experiment agents used with the intent to perturb the HIV-1 viral reservoir.17. History of seizures, psychosis, abnormal electroencephalogram or brain damage with significant persisting neurological deficit18. Positive test for tuberculosis by either skin test (PPD) or blood interferon-gamma release assay (QuantiFERON).19. Significant substance use, which in the opinion of the investigator(s), is likely to interfere with the conduct of the study.
TEST PRODUCT, DOSE, AND ROUTE OF ADMINISTRATION	1 g of Euphorbia kansui extract powder, measured and reconstituted in 4 fluid ounces of boiled water allowed to cool and administered as tea, taken by mouth daily as either a single or 3 consecutive daily doses.
CONTROL PRODUCT, DOSE AND ROUTE OF ADMINISTRATION	Cohort 1: no placebo. Cohort 2: a placebo treatment arm will be assigned to patients in a randomized crossover design. The placebo will be decaffeinated black loose leaf tea which produces a tea that is similar in appearance, consistency, and (bitter) taste to kansui extract powder, without any known immune modulating properties or drug-drug interactions (e.g., changes in pH balance that might affect drug absorption) with HIV antiretroviral therapy.

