8.3.3 Packaging and Labeling

The University of Utah Health Investigational Drug Service (UUH IDS) Pharmacy will prepare individual 1 g doses *Euphorbia kansui* extract powder or placebo using a Ohaus® Pharmacy Scale w/ Internal Calibration. As kansui (the root of *Euphorbia kansui*) is a Chinese herb with known safety issues, all laboratory and clinical personnel who handle kansui extract powder must use proper personal protection equipment (specifically - facemask, labcoat, and gloves) to prevent potential allergic reactions (e.g., contact dermatitis). Preparations will be packaged in white HDPE (high density polyethylene plastic) vials with screw caps and a tight, leakproof inner seal. Each study preparation bottle will be labeled with the required FDA warning statement, the protocol number, study participant number, a visit number, and directions for patient use.

Hunstman Cancer Hospital IDS
[name] [contact]

RX: xxxxx-x

Prescriber name

Date

Subject ID: xxxxxxxx

Protocol#: Kansui

Subject full name:

Mix 1 gram of powder in 4 ounces of warm water and ingest by mouth as directed. *Euphorbia kansui* extract powder or placebo.

Qty: 1 gram

Rt: oral Do not use after: "expiration date"

Refills: 0

Caution: Drug limited by Federal (United States) Law to investigational use only

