8.4.3 Administration Instructions

Study Investigators will instruct study staff on how to prepare the *Euphorbia kansui* extract powder as a tea, per traditional Chinese medicine practice as outlined in the *Euphorbia kansui* Extract Tea Preparation Guidance SOP.

Study staff will dispense and observe study participant take 1 vial (1 g) of *Euphorbia kansui* extract powder in 4 mL of water prepared as follows:

- a. One gram of *Euphorbia kansui* extract from the labeled vial will be placed into a 6-ounce Styrofoam or paper cup.
- c. Four ounces of boiled water cooled to 170-185° F will be added to the powder in cup. Research staff will measure the water temperature using a designated thermometer for tea use only.
- d. The tea will be stirred for approximately 30 seconds using a wooden stirring stick.

- e. The tea will be allowed to cool for at least 5 minutes, reaching a temperature of less than or equal to 100° F, before administration.
- f. All contents in the cup will be checked to ensure that the powder and water have been stirred appropriately and fully consumed. Research staff will record the time of dose (Time 0) on the treatment flowsheet.
- g. Specific restrictions will be followed: no ice-cold beverages below <40°F) but graham crackers and room temperature juice will be allowed after the kansui dose (up to three servings of each), but other food & beverages will be restricted until AFTER 2+hr post-dose draw.

Study staff will then observe administration and side effects of participants on the day(s) of kansui treatment.

Study staff will similarly dispense and observe study participant take 1 packet of 100% pure decaffeinated black tea in 4 mL of water prepared as follows:

- a. One packet of Twinings English breakfast 100% pure black decaffeinated tea from the labeled vial will be place into a 6-ounce Styrofoam or paper cup.
- c. Four ounces of boiled water cooled to 170-185° F will be added to the tea in cup. Research staff will measure the water temperature using a designated thermometer for tea use only.
- d. The tea will be stirred for approximately 30 seconds using a wooden stirring stick.
- e. The tea will be allowed to cool for at least 5 minutes, reaching a temperature of less than or equal to 100° F, before administration.
- f. All contents in the cup will be checked to ensure that the tea and water have been stirred appropriately and fully consumed. Research staff will record the time of dose (Time 0) on the treatment flowsheet.

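### The placebo has three different forms across the protocol, and no step makes the served drink look like kansui, which puts the Cohort 2 blind at risk

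*Combined protocol and SAP*

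**What the plan says.** Cohort 2 is a randomized, double-blind crossover in which six participants each take kansui on three days and placebo on three days (section 4.1, section 8.4.1).

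The placebo is described in several places:

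- **Synopsis, control product:** "The placebo will be decaffeinated black loose leaf tea which produces a tea that is similar in appearance, consistency, and (bitter) taste to kansui".
- **Section 8.3.2:** cooled boiled water is "added to the tea bag in a cup". The tea is then "stirred for approximately 30 seconds using a wooden stirring stick and allowed to cool for at least 5 minutes" before it is given.
- **Section 8.4.3:** the cup receives "One packet of Twinings English breakfast 100% pure black decaffeinated tea from the labeled vial". Water, stirring and cooling follow. The check before hand-over reads "All contents in the cup will be checked to ensure that the tea and water have been stirred appropriately and fully consumed".
- **Section 8.3.3:** the pharmacy prepares 1 g doses of "extract powder or placebo using a Ohaus® Pharmacy Scale w/ Internal Calibration". The vial label, shared by both products, reads "Mix 1 gram of powder in 4 ounces of warm water and ingest by mouth as directed".
- **Section 8.4.1:** the dose is one gram of kansui powder or placebo, made up in water.

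Kansui itself is powder stirred into the water in the cup (section 8.4.3).

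On blinding, section 8.2 provides identical vials and has the nurse make the tea in the med room, out of sight of the participant, the coordinator and the site investigator. Section 8.3.2 adds a separate room so that participants do not see differences in preparation and packaging.

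**The concern.** Loose leaves, an intact bag or packet, and a weighed gram are different products to dispense. They may also be different drinks to look at. A pharmacist working from section 8.3.3 and a nurse working from section 8.4.3 would expect different contents in the same vial. The protocol gives no packet weight, so one packet and one gram cannot be equated.

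Blinding in a crossover depends on the drink in the participant's hand, because each person meets both products and can compare them. Safety and tolerability is the primary endpoint. Most of the solicited events in section 10.4, such as gastrointestinal irritability, headache and light-headedness, depend largely on what participants report. Relatedness is then judged under section 10.1 and by the team under section 13, and drug-related events feed the pausing and discontinuation criteria in section 10.4. If the two drinks can be told apart, both the reports and the attributions lose the protection that the placebo phase was added to give.

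**Working it through.** The protocol states no figure on this point, so the check sets the relevant sections side by side.

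**1. Form and quantity of the placebo**

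| Section | Form | Quantity | Similarity to kansui stated? |
|---|---|---|---|
| Synopsis, control product | Loose leaf | None given | Yes |
| 8.3.2 | Tea bag (also called a packet) | One packet | No |
| 8.4.3 | Packet, taken from the vial | One packet | No |
| 8.3.3 | Weighed dose | 1 g | No |
| 8.4.1 | Dose made up in water | 1 g | No |

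These reduce to three forms: loose leaf, bag or packet, and weighed dose. The similarity claim is attached to one of them, and it is not the form in the preparation instructions.

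**2. From adding water to drinking**

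Section 8.2 sends the nurse to section 8.4.3 for administration. That section goes: packet in cup, water, stir for about 30 seconds, cool for at least 5 minutes, check, give. Section 8.3.2 has the same sequence. Neither removes a bag or strains leaves. The step lettering in section 8.4.3 runs from a to c, but the missing letter falls before water is added, so it cannot be a lost removal step.

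**3. What each safeguard covers**

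| Safeguard | Covers | Covers the finished drink? |
|---|---|---|
| Identical vials (8.2) | Packaging | No |
| Preparation out of sight (8.2) | Preparation | No |
| Separate room (8.3.2) | Preparation and packaging, from participants | No |
| Same Styrofoam or paper cup for both (8.4.3) | Sides of the cup, if opaque | Partly; no lid is mentioned |

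No section describes a check that the two finished drinks look alike. Section 8.4.3 also has study staff observe administration and side effects, so participants are not the only people who may see the cup.

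**4. Exposure**

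Six participants with three placebo days each give 6 × 3 = 18 placebo servings, and the same number of kansui servings. This counts the servings at risk. It is not an estimate of bias.

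**The case against.** The case on the other side has several parts, and much of it stands.

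- **A reader might infer that the bag stays in the cup.** The protocol does not say so. It only omits a removal step, and staff might remove the bag as a matter of course.
- **A reader might infer that the consumption check is impossible to meet with a bag in the cup.** The wording does not support this. What has to be stirred and consumed is the tea and water, not the bag.
- **A reader might take the label as proof of a powdered placebo.** A blinded label has to read the same for both products, so its reference to powder does not define the placebo. The conflict in sections 8.3.3 and 8.4.1 is one of quantity and preparation: a weighed gram against one packet.
- **A reader might infer that the drinks do look different and that the phase is revealed.** No section describes how prepared kansui looks. The only statement on appearance, in the synopsis, says the teas are similar. It belongs to the loose leaf form and no supporting check is described, but nothing in the text contradicts it directly.
- **The common cup narrows the risk.** Both products already go into the same type of cup, whose walls may well be opaque.
- **Serving details may sit in the preparation SOP.** That SOP is cited but not supplied. Its title and description concern kansui, and no placebo SOP is cited.
- **The analysis is not built on the blinded comparison of events.** Section 14.3 tabulates adverse events by dosing cohort and plans no kansui-versus-placebo test. The secondary endpoints are flow cytometry and HIV RNA assays.
- **The drug effect may unblind anyway.** Section 2 expects bowel elimination within two hours of a single 1 g dose.

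These points limit the claim but do not remove it. The forms still conflict, and no safeguard fully covers the finished drink.

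**Conclusion.** The inconsistency is certain: loose leaf, bag or packet, and a weighed 1 g dose all stand in the current text, and the similarity claim belongs only to the first. The blinding consequence is a risk, not a documented failure. It rests on two assumptions: that staff follow section 8.4.3 literally, and that the unsupplied SOP does not add a removal or matching step for the placebo.

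The risk covers all six Cohort 2 participants. It falls mainly on self-reported tolerability and on relatedness judgements. T-cell activation and HIV RNA are much less exposed, and no planned hypothesis test of adverse events between kansui and placebo is affected. The documents give no basis for putting a number on the bias. It is worth correcting because the correction is cheap, not because the design fails without it.

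**What to change.** 1. Reconcile the synopsis and sections 8.3.2, 8.3.3, 8.4.1 and 8.4.3 to a single placebo form and quantity. If the similarity claim is kept, attach it to that form.
2. State in sections 8.3.2 and 8.4.3 that any bag or leaves are removed or strained in the med room before the drink is handed over.
3. Serve both products in the same type of cup with a lid.

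While section 8.4.3 is open, reconcile the water volume as well: the lead-in to each list says 4 mL and the steps say four ounces.

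The cost is a wording change, lids and one short extra preparation step. The change does not remove every cue: taste, texture and the effect of kansui itself may still reveal the phase.
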